Appendix D
New York Heart Association (NYHA) Classification

NEW YORK HEART ASSOCIATION (NYHA) CLASSIFICATION

The NYHA classification will be based on the following definitions:

- Class I No limitation:

 Ordinary physical exercise does not cause undue fatigue, dyspnoea or palpitations.
- Class II Slight limitation of physical activity:

 Comfortable at rest but ordinary activity results in fatigue, palpitations, dyspnoea.
- Class III Marked limitation of physical activity:

 Comfortable at rest but less than ordinary activity results in symptoms.
- Class IV Unable to carry out any physical activity without discomfort:

 Symptoms of congestive heart failure are present even at rest with increased discomfort with any physical activity.

Clinical Study Protocol Appendix E

Drug Substance	Dapagliflozin
Study Code	D1692C00006
Edition Number	1
Date	

Appendix E
Algorithm on Management of Hyponatraemia

ALGORITHM ON MANAGEMENT OF HYPONATRAEMIA

If a patient experiences a serum sodium ≤ 125 mmol/L, with or without symptoms, dosing of blinded investigational product will be interrupted. A repeat serum sodium concentration will be drawn within 3 days of the receipt of the result.

- If the repeat sodium concentration within 3 days is ≥ 130 mmol/L

Investigational product may be restarted unless otherwise contraindicated. Serum sodium will be rechecked in 7 days after restarting the investigational product.
 - If the repeat sodium concentration within 7 days of restarting the investigational product is < 130 mmol/L, investigational product will be discontinued. Patients will have an end of treatment visit and a follow-up visit three weeks after discontinuation of investigational product as specified in Section 5.8.2 in the CSP.
 - If the repeat sodium concentration within 7 days of restarting the investigational product is ≥ 130 mmol/L, further management should be based on composite of sodium concentration, clinical assessment of the patient and an evaluation of underlying cause of hyponatraemia.

- If the repeat sodium concentration within 3 days is < 130 mmol/L

If there is **no** suspected new, temporary, and reversible cause of hyponatraemia based on clinical assessment (other than investigational product), investigational product will be discontinued. Patients will have an end of treatment visit and a follow-up visit three weeks after discontinuation of investigational product as specified in Section 5.8.2 in the CSP.

If there is a suspected new, temporary, and reversible cause of hyponatraemia based on clinical assessment (other than investigational product), investigational product will continue to be interrupted. The suspected cause of hyponatraemia should be identified and corrected. The serum sodium will be rechecked in another 7 days.
 - If the repeat sodium concentration within 7 days is < 130 mmol/L, investigational product will be discontinued. Patients will have an end of treatment visit and a follow-up visit three weeks after discontinuation of investigational product as specified in Section 5.8.2 in the CSP.
 - If the repeat sodium level concentration within 7 days is ≥ 130 mmol/L investigational product may be restarted unless otherwise contraindicated. Serum sodium will be rechecked in 7 days after restarting the investigational product, and further management should be based on composite of sodium

concentration, clinical assessment of the patient and an evaluation of underlying cause of hyponatraemia.

For patients whose serum sodium is in the range of 126-129 mmol/L, the investigator's clinical judgment should apply concerning whether such patients should be entered into this algorithm.

Clinical Study Protocol: Appendix F

Drug Substance	Dapagliflozin
Study Code	D1692C00006
Edition Number	1
Date	

Appendix F
Case Identification and Management of Decreased Renal Function

CASE IDENTIFICATION AND MANAGEMENT OF DECREASED RENAL FUNCTION

In order to standardise the definition and management of decreased renal function, the following guideline has been developed. Please note separate sections for patients who are treated with metformin and for those who are not treated with metformin.

FOR PATIENTS WHO ARE TREATED WITH METFORMIN:

If calculated eGFR is <60 ml/min or if there is an increase in serum creatinine of ≥ 0.5 mg/dL (≥ 44.2 $\mu\text{mol/L}$) above the baseline value based on central laboratory results, this will be considered a case of “decreased renal function”.

In this circumstance, the investigator should consider evaluating the patient for potentially reversible causes of renal dysfunction including:

1. concurrent use of NSAIDS, antibiotics, or other medications known to affect measures of serum creatinine
2. volume depletion
3. urinary tract infection
4. obstructive uropathy.

Patients should return for repeat central laboratory testing as soon as possible, no later than 7 days after the abnormal result. Investigational drug and metformin should be interrupted pending the results of repeat testing. If after interruption eGFR is still <60 ml/min or if the serum creatinine value remains ≥ 0.5 mg/dL (≥ 44.2 $\mu\text{mol/L}$) above the baseline value, the patient should permanently discontinue the study medication and be withdrawn from the study (in which case an Adverse Event must be reported).

If after interruption of investigational drug and metformin eGFR is ≥ 60 ml/min or if the serum creatinine value has decreased to <0.5 mg/dL (<44.2 $\mu\text{mol/L}$) above baseline, investigational drug and metformin can be re-started if appropriate in the judgement of the investigator and following consultation with the study team physician. If the patient restarts investigational drug and metformin and eGFR is again <60 ml/min or the serum creatinine value increases again to ≥ 0.5 mg/dL (≥ 44.2 $\mu\text{mol/L}$) above baseline, the patient should permanently discontinue the study medication and be withdrawn from the study (in which case an Adverse Event must be reported).

FOR PATIENTS WHO ARE NOT TREATED WITH METFORMIN:

If a) eGFR is <45 ml/min or b) in subjects with baseline creatinine ≥ 1.4 mg/dL (≥ 123 $\mu\text{mol/L}$) there is an absolute increase in serum creatinine of ≥ 1.0 mg/dL (≥ 88 $\mu\text{mol/L}$), or c) in subjects with baseline creatinine <1.4 mg/dL (<123 $\mu\text{mol/L}$) there

is an absolute increase in serum creatinine of ≥ 0.5 mg/dL (≥ 44 μ mol/L), this will be considered a case of “decreased renal function”.

In this circumstance, the investigator should consider evaluating the patient for potentially reversible causes of renal dysfunction including:

1. concurrent use of NSAIDS, antibiotics, or other medications known to affect measures of serum creatinine
2. volume depletion
3. urinary tract infection
4. obstructive uropathy.

Patients should return for repeat central laboratory testing as soon as possible, no later than 7 days after the abnormal result. Investigational drug should be interrupted pending the results of repeat testing. If after interruption eGFR is still < 45 ml/min or if the serum creatinine value remains ≥ 0.5 mg/dL (≥ 44.2 μ mol/L) above the baseline value, the patient should permanently discontinue the study medication and be withdrawn from the study (in which case an Adverse Event must be reported).

If after interruption of investigational drug eGFR is ≥ 45 ml/min or if the serum creatinine value has decreased to < 0.5 mg/dL (< 44.2 μ mol/L) above baseline, investigational drug can be re-started if appropriate in the judgement of the investigator and following consultation with the study team physician. If the patient restarts investigational drug and eGFR is again < 45 ml/min or the serum creatinine value increases again to ≥ 0.5 mg/dL (≥ 44.2 μ mol/L) above baseline, the patient should permanently discontinue the study medication and be withdrawn from the study (in which case an Adverse Event must be reported).

Clinical Study Protocol Appendix G

Drug Substance	Dapagliflozin
Study Code	D1692C00006
Edition Number	1
Date	

Appendix G
Algorithm on Management of Sustained Elevated Liver Safety
Abnormalities

ALGORITHM ON MANAGEMENT OF SUSTAINED ELEVATED LIVER SAFETY ABNORMALITIES

The monitoring for liver safety will be performed using the serum levels of AST, ALT and TB (see [Figure 1](#) Sustained Elevated Liver Safety Abnormalities flow chart).

Patients with a central laboratory ALT and/or AST >3 X ULN will be scheduled for a follow-up visit within 3 days following receipt of the initial laboratory results, to obtain repeat central laboratory ALT, AST, TB and Alkaline Phosphatase (ALK-P). In the event that the repeat laboratory assessments cannot be obtained within 3 days, the Investigator is encouraged to discuss possible alternatives with the Sponsor. Patients should remain on study medication until confirmatory results are obtained, unless otherwise contraindicated.

- **If the repeat ALT and AST are $\leq 3X$ ULN**, patient should continue double-blind treatment according to their original visit schedule unless otherwise contraindicated.
- **If the repeat ALT and/or AST are $>3X$ ULN but $\leq 8X$ ULN and TB $\leq 1.5X$ ULN**, the patient's medical history, including details of risk factors for liver diseases, should be evaluated for potential underlying aetiologies. In addition, specialized blood sampling will be performed to evaluate liver function as well as identify potential causes of laboratory elevation(s). The Investigator should continue to monitor the patient's liver tests every 3 days following receipt of the prior laboratory results until the ALT and AST are $\leq 2X$ ULN or until ALT and AST are at or below baseline levels. The frequency of retesting can decrease to once a week or less if abnormalities stabilize and the patient is asymptomatic. Patients should remain on study medication unless confirmatory results indicate that a criterion for discontinuation has been met or continuing study medication would be otherwise contraindicated.

Patients must be discontinued from the study if an initial and repeat confirmatory laboratory tests meet any of the following criteria:

- ALT and/or AST are >3 x ULN and TB >1.5 x ULN
- ALT and/or AST are >5 x ULN for ≥ 14 consecutive days, at any time after initial confirmatory results
- ALT and/or AST are >8 x ULN

In each of these situations, study medication will be discontinued, the Sponsor notified and the End of Treatment Visit performed within 3 days of the confirmed laboratory results (see Section 5.8.2 in the CSP). At the End of Treatment Visit, medical history including details of risk factors for liver diseases (if not previously assessed) will be requested and additional

blood sampling performed (**Specialized Liver Panel and Liver Discontinuation Panel**, see detailed below). Patient should also be scheduled for a Follow-up Visit (ie, procedures of Visit 14) 3 weeks after discontinuation of investigational product. A referral consultation to a hepatologist or gastroenterologist (specializing in liver abnormalities) should be obtained.

Any additional tests and/or examinations should be carried out at the discretion of the Investigator. Any further investigations and laboratory results for patients with abnormal laboratory values at the Follow-up Visit should be made available to the Sponsor upon request.

Additional information, including but not limited to completion of supplemental eCRFs may be requested for certain adverse events and/or laboratory abnormalities which are reported/identified as part of the hepatic safety surveillance.

Following the End of Treatment Visit, the Investigator should continue to monitor the subject's liver tests every 3 days following receipt of the prior laboratory results until the ALT and AST are $\leq 2 \times$ ULN or until ALT and AST are at or below baseline levels. The frequency of retesting can decrease to once a week or less if abnormalities stabilize and the subject is asymptomatic.

Guidance on Assessment of Hepatic Laboratory Abnormalities

The following is presented to assist in the evaluation and management of hepatic laboratory values. It is not intended to supplant Investigators' clinical judgment.

Patients who experience ALT and/or AST values $>3 \times$ ULN confirmed with a repeated test will have the following performed within 3 days of the confirmed laboratory results:

- AE assessment
- Physical Examination for jaundice and other signs of liver diseases
- Review of relevant risk factors and current history focusing on possible causes of the increased ALT and/or AST and/or TB, including:
 - Use of suspect concomitant medication [including over-the-counter (ie, acetaminophen/paracetamol), herbal and vitamin preparations]
 - Recent alcohol consumption or recreational drug/narcotic use
 - Recent unaccustomed physical exertion
 - Occupational or environmental exposure to hepatotoxins
 - Other conditions which may cause liver diseases or which may cause abnormal test results

- Specialized Liver Laboratory Panel (see below)

Specialized Liver Panel

For patients who are being monitored frequently as a result of confirmed AST and/or ALT >3X ULN, additional central laboratory tests will be performed within 3 days of receipt of confirmatory results. These laboratory tests will study the possible causes of the increased ALT and/or AST and/or TB, and may include, but are not limited to, the following tests:

- Hepatitis A IgM
- Hepatitis BsAg
- Hepatitis B Core Ab IgM
- Hepatitis C virus RNA
- Hepatitis C Ab
- Hepatitis E IgM
- Epstein-Barr Virus (EBV) IgM Ab
- Lactate Dehydrogenase (LDH)
- Gamma-glutamyl-transpeptidase (GGT)
- Carbohydrate deficient transferrin (CDT)
- Prothrombin time (PT/INR)
- Iron Panel - iron, ferritin, total iron binding capacity (TIBC)
- Immunology Panel including Antinuclear Antibody (ANA), Anti-Smooth Muscle Antibody (SMA) and Anti-Liver/Kidney Microsomal Antibody (Anti-LKM)
- Anti-tissue Transglutaminase Antibody

Liver Discontinuation Panel

[figure not shown]
For patients who are discontinued from the study as a result of sustained elevated liver safety abnormalities, additional central laboratory tests will be performed at the time of End of Treatment Visit. Similar to the Specialized Liver Panel, these laboratory tests will study the possible causes of the increased ALT and/or AST and/or TB, and may include, but are not limited to, the following tests:

- Cytomegalovirus (CMV) IgM Ab

- Herpes Simplex Virus (HSV) 1 and 2
- Ceruloplasmin
- Toxoplasmosis
- Alpha-1 antitrypsin

For specific details regarding the Specialized Liver Panel or the Liver Discontinuation Panel laboratory tests, refer to the Central Laboratory Manual for this study.

Figure 1 Sustained elevated liver safety abnormalities flow chart

- a In patients with repeat ALT or AST > 3X ULN but ≤ 8X ULN, only patients with TB ≤ 1.5X ULN at Step 1 should be followed according to Step 2b. Patients with an initial TB and confirmatory repeat TB > 1.5X ULN should be followed according to Step 2d.

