5.8.2 Procedures for discontinuation of a subject from investigational product

A subject that discontinues will always be asked about the reason(s) for discontinuation and the presence of any AEs. The Principal Investigator/sub-investigator will perform the best possible observation(s), test(s) and evaluation(s) as well as give appropriate medication and all possible measures for the safety of the subject. They will also immediately inform AstraZeneca of the withdrawal. AEs will be followed up (See Sections 6.4.3 and 6.4.4); diary, glucometer and study drug should be returned by the subject.

Randomised subjects

Randomised subjects who discontinue the study treatment before Week 24 should return and complete the procedures described for Visit 13 as soon as possible but at the latest 7 days after discontinuation. These subjects should also be scheduled for a follow-up visit (ie, procedures of Visit 14) three weeks after discontinuation of investigational product. In addition subjects who discontinue the study due to an AE including a laboratory abnormality should be followed by the investigator until the event has been resolved or stabilised.

After discontinuation of investigational product alternative anti-diabetic treatment will be initiated according to the investigator's judgement and according to local medical practice.

Subjects with an increased CK >10X ULN will have their investigational product held and repeated CK test preferably within 24 hours, but not exceeding 72 hours. If repeated CK is still >10X ULN the subject should permanently discontinue all study medication and be withdrawn from the study (in which case an Adverse Event must be reported). Otherwise investigational product may be resumed unless otherwise contraindicated.

Subjects with increased liver function tests as defined in Section 5.8.1 under listing No.13 will be scheduled for a follow-up visit within 3 days following the receipt of the result. Subjects may remain on study medication until the confirmatory results are obtained. If repeat liver function tests still are increased as outlined in Appendix G the subject should permanently discontinue study medication and be withdrawn from the study (see Appendix G for further guidance).

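### Appendix G lets on-drug liver retesting drop to weekly or less with no 5X ULN ceiling and no test tied to day 14, so the mandatory 14-day stop can be reached late

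*Protocol*

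**What the plan says.** Appendix G handles a repeat ALT and/or AST above 3X and up to 8X ULN, with total bilirubin at or below 1.5X ULN, as a single on-drug branch. Tests are to be repeated "every 3 days following receipt of the prior laboratory results" until ALT and AST are at or below 2X ULN or back to baseline levels. The relaxation follows: "The frequency of retesting can decrease to once a week or less if abnormalities stabilize and the patient is asymptomatic". On drug status the branch says: "Patients should remain on study medication unless confirmatory results indicate that a criterion for discontinuation has been met", with an exception where continuing is otherwise contraindicated.

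The stopping rule comes directly below: "Patients must be discontinued from the study if an initial and repeat confirmatory laboratory tests meet any of the following criteria". The second criterion is ALT and/or AST above 5X ULN for at least 14 "consecutive days, at any time after initial confirmatory results". Section 5.8.1 item 13(b) repeats it without a retest schedule. Section 5.8.2 deals only with the first repeat ("Subjects may remain on study medication until the confirmatory results are obtained") and then refers to Appendix G.

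Appendix G gives almost the same permission after the End of Treatment Visit: "The frequency of retesting can decrease to once a week or less if abnormalities stabilize and the subject is asymptomatic". Those subjects are already off drug.

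**The concern.** A rule based on duration can be shown to be met only by a test taken once that duration has elapsed. None of the readable text in Section 5.8.1, Section 5.8.2 or Appendix G requires a test at that point. The relaxation has two conditions, stable values and no symptoms, and neither refers to 5X ULN. A persistent value between 5X and 8X ULN is what the 14-day criterion exists to catch, and it is also a value that an investigator could fairly call stable. Using the stated permission breaks no visible rule, yet it can carry the subject past a mandatory stop on blinded drug.

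Other safety algorithms in the protocol are tighter. Appendix E (sodium) fixes rechecks at 3 and 7 days, with drug interrupted when the low value is found. Appendix F (renal function) requires a repeat within 7 days with drug interrupted. Section 5.8.2 holds drug for CK above 10X ULN and requires a repeat within 72 hours. After the End of Treatment Visit the relaxed liver retesting does no harm, because no stopping clock is running. In the on-drug branch a clock is running.

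**Working it through.** **Inputs from the protocol.** Mandatory stop: above 5X ULN for at least 14 consecutive days (Appendix G; Section 5.8.1 item 13(b)). Default interval: 3 days after receipt of the prior result (Appendix G). Permitted interval: once a week or less often (Appendix G).

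**Assumptions.** Day 0 is the first value above 5X ULN that is later confirmed. The value then stays above 5X and at or below 8X ULN, with bilirubin at or below 1.5X ULN. Laboratory turnaround is not given in the protocol; it is taken as 0 to 3 days for the default schedule and as 0 for the relaxed ones.

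**Formula.** Overrun = (first test day on or after day 14) − 14.

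**Default schedule.** With turnaround t the interval is 3 + t days.
- t = 0: tests on days 3, 6, 9, 12, 15; overrun 15 − 14 = 1.
- t = 1: days 4, 8, 12, 16; overrun 2.
- t = 2: days 5, 10, 15; overrun 1.
- t = 3: days 6, 12, 18; overrun 4.

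The default therefore runs 1 to 4 days over.

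**Relaxed schedules.** Testing is every 3 days up to day d, then at the longer interval.

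| Last 3-day test (d) | Weekly: first test on or after day 14 | Overrun | 14-day spacing: first test on or after day 14 | Overrun |
|---|---|---|---|---|
| 3 | 3 + 7 + 7 = 17 | 3 | 3 + 14 = 17 | 3 |
| 6 | 6 + 7 + 7 = 20 | 6 | 6 + 14 = 20 | 6 |
| 9 | 9 + 7 = 16 | 2 | 9 + 14 = 23 | 9 |
| 12 | 12 + 7 = 19 | 5 | 12 + 14 = 26 | 12 |

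Weekly testing runs 2 to 6 days over and 14-day spacing 3 to 12 days over. Strict weekly testing from day 0 gives days 7 and 14, with no overrun.

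**Sensitivity to turnaround.** If turnaround also lengthens the early 3-day tests, and the interval is relaxed after the second of them, then t = 1 puts that test on day 8. Weekly gives day 15 (1 over) and 14-day spacing gives day 22 (8 over). With t = 2 it falls on day 10, giving day 17 (3 over) and day 24 (10 over).

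**Sensitivity to the clock.** If the 14 days are counted from a confirmatory test on day 3, the limit is day 17. For d = 6, both weekly testing and 14-day spacing first reach the limit on day 20, 3 days over; the 3-day default reaches it on day 18, 1 day over. The delay is smaller here but does not disappear.

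**The case against.** The strongest objection is that the flow chart governing this branch is not in the readable text. A footnote to Figure 1 says that subjects in the 3X to 8X ULN band with bilirubin at or below 1.5X ULN "should be followed according to Step 2b", and the content of that step cannot be seen. It may hold a limit. This stands as a limit on the claim, which is confined to the visible text. It does not remove the point: a tighter interval found only in the figure would conflict with the permission in the prose, and one of the two would have to change.

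Second, the permission is optional and sits beside a separate mandatory stop. A reader might infer that Appendix G contradicts itself or overrides the stop. It does neither. The stop remains in force; what is missing is the test that would trigger it on time.

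Third, any duration rule checked by intermittent sampling is detected a little late, and the ranges for weekly testing (2 to 6 days) and the default (1 to 4 days) overlap. This also stands. Under literal weekly testing the added delay is only a few days.

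A reader might go further and infer delays of several weeks, by supposing that no extra test is done until the next 4-weekly safety panel. The documents do not support that. Appendix G tells the investigator to go on monitoring until values fall to 2X ULN or to baseline levels; the permission lowers the frequency and does not end the testing. A value that has just crossed 5X ULN has also not stabilised, so the 3-day default applies at that moment.

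Finally, there are backstops. Separate stops apply above 8X ULN, and above 3X ULN with bilirubin above 1.5X ULN. Section 5.8.1 items 2 and 6 allow discontinuation on judgement of risk or for a laboratory abnormality. Section 4.2 criterion 13 excludes AST or ALT above 3X ULN at Visit 1, so few subjects should be affected.

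**Conclusion.** The point holds as a minor subject-safety weakness. On the visible text, a stable, asymptomatic ALT or AST above 5X ULN may be tested weekly or less often while the subject stays on drug, and nothing ties a test to day 14. The mandatory stop would then be recognised about 2 to 6 days late with weekly testing begun after some 3-day tests, and about 3 to 12 days late with 14-day spacing, against about 1 to 4 days under the default.

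These figures assume that the value persists between 5X and 8X ULN with bilirubin at or below 1.5X ULN, that the investigator uses the permission, and that Figure 1 contains no tighter rule. The protocol gives no rate for such elevations and none is claimed here.

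It would be wrong to read this as a threat to the efficacy analysis or to hepatic adjudication. Section 6.4.16 sends liver laboratory abnormalities to the committee in their own right, as well as hepatic disorders that lead to discontinuation.

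**What to change.** Keep the repeat within 3 days, the 3-day default and the stability and no-symptom conditions as they are. Add to the on-drug branch of Appendix G:
- While ALT or AST is above 5X ULN on drug, the relaxed interval may not exceed one week.
- A liver test must be done on day 14 (window day 14 to 16), counted from the first value above 5X ULN that is later confirmed, and drug is stopped if the value is still above 5X ULN.
- Intervals longer than a week are allowed only when ALT and AST are both at or below 5X ULN.

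Check Figure 1 and align it. The 5X ULN level and the 14-day duration do not change. The overrun becomes at most 16 − 14 = 2 days plus laboratory turnaround.

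The cost is one or two sentences and one or a few extra liver tests compared with the relaxed schedule. It remains within the existing default. With zero turnaround the default needs 5 retests to reach the stop (days 3, 6, 9, 12 and 15). The amended schedule needs 3 if weekly testing starts after day 3 (days 3, 10 and 14 to 16), and at most 5 if it starts after day 12 (days 3, 6, 9, 12 and 14 to 16).
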